Expected outcomes. Findings from Aim 2 will advance our understanding of the uptake and impact of peer-led interventions for people living with HIV. Crucially, we will identify populations of men who do not respond to the Coach Mpilo program. We will gain insights from both recipients of the intervention and coaches on perceived efficacy and underlying mechanisms for intervention effects determined in Aim 1. Findings will inform intervention scale-up and modifications to the program for maximum impact.

IDI quality assurance: We will monitor depth of discussions through immediate review of interview materials, and if necessary, refine probes in the IDI guides, and conduct additional interviewer training.

Aim 3: Assess the cost-effectiveness of the Coach Mpilo program

To inform strategic policy decisions about the scale-up of Coach Mpilo, and how it compares in cost and cost-effectiveness against current standard of care treatment, as well as other HIV interventions, we will conduct an economic evaluation. We will collect cost-related data and resource utilization data to construct cost estimates for both arms. These data will be combined with retention in care data from Aim 1 to determine average costs per client retained in care and incremental cost per additional person retained. As part of the analysis, we will conduct a sub-analysis to adjust the cost estimates to reflect implementation in a routine care setting, excluding research-related expenses such as start-up and study-specific costs. This will provide more realistic national-level scale-up cost estimates for Coach Mpilo. Epidemiological modeling based on effectiveness estimates from Aim 1, will use the Thembisa model¹⁵ to estimate several long-term health outcomes, including life years saved and HIV infections averted due to onward transmission. These long-term health outcomes will form the basis to estimate the cost-effectiveness analysis of Coach Mpilo. To compare Coach Mpilo to other HIV prevention and treatment options in South Africa with the broader aim of informing strategic policy decisions, we will incorporate our estimates into the South Africa HIV Investment Case, a prominent initiative that assesses the relative cost-effectiveness of different HIV interventions and aims to inform government of the optimal mix of interventions that also accounts for allocative efficiency.

Cost and resource use data sources

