A detailed overview of individual cost categories, their associated expenditures, and required resources is provided below, with a consolidated summary presented in Table 1.

Start-up costs

Information on the cost of training of coaches and other personnel or volunteers involved in Coach Mpilo will be obtained from Matchboxology. This information will include the number of participants attending the training (for the economic costing, the opportunity cost of their time will be based on their salary), the total cost of organising a workshop and the number of workshops held. The cost per person trained will consider expenses related to the development of training materials, refreshments, office supplies, facilitator, etc.

Staff costs

Staff costs will be based on public sector clinic staff salaries (from Department of Public Service and Administration), and implementer's records of coaches' and squad manager salaries. Staff who do not provide direct patient care, but who support the running of the programme, such as admin staff, will also be included. Time spent by coaches in engaging with intervention recipients will be determined through log-books maintained by the coaches during intervention implementation, presented in Appendix F. Time spent with patients at clinic-level will be sourced

from existing time and motion data for patients on treatment in studies previously conducted by HE²RO.

Laboratory costs

Laboratory test costs will be sourced from the National Health Laboratory Service (NHLS), while quantities of tests will be sourced from a combination of client medical records at the clinic, data from TIER.Net and latest ART guidelines.

Drug costs

Drug costs, both ARV and non-ARV, will be sourced from the National Department of Health's (NDoH) Master Product Health List, which contains prices from national government tenders for all drugs available in the public sector. The quantities of drugs will be sourced from a combination of client medical records at the clinic, data from TIER.Net and latest ART guidelines.

Consumables and equipment

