Equipment	For clinics: National Treasury and NDOH contracts, clinic financial records, retail pricing For coaches: Matchboxology for coaches.	For clinics: Existing literature for clinics For coaches: Matchboxology for coaches.
Building/space overheads (incl utilities)	For clinics: Department of Health, clinic financial records, existing literature	For clinics: Clinic financial records, existing literature For coaches: Matchboxology for coaches.
Other start-up costs	Training for coaches: Costs from Matchboxology	Training for coaches: Quantities from Matchboxology

Time horizon and discounting

The timeframe for the costs will be annual, with annualization of capital resources that provide benefits for more than one year. We will consider depreciation of equipment and building (cost allocation of a tangible asset over its useful life) using a discount rate of 5%. For the intermediary cost-effectiveness analysis, the time horizon will be 1 year, in line with the Aim 1 outcomes for Coach Mpilo. For long-term impact modelling and cost-effectiveness analysis, we will consider a 20-year time horizon. Costs and outcomes will be presented undiscounted over the 20-year time horizon, with sensitivity analyses applying different discount rates that are relevant to policymakers (commonly, 3% and the current repo rate as informed by the South African Reserve Bank).

Analyses

The analyses will be conducted in three phases:

- 1) **Cost analysis:** we will utilize a multiprong approach that incorporates top-down and bottom-up costing methodologies to construct a cost for both standard of care and Coach Mpilo arms.

- 2) **Cost-effectiveness analysis:** we will conduct both intermediate and long-term cost effectiveness analysis (using an HIV transmission model), comparing Coach Mpilo to standard of care.
- 3) **Integration into the HIV Investment Case:** we will compare the cost-effectiveness of Coach Mpilo to other HIV prevention and treatment options in South Africa to inform strategic policy decisions for the South African government.

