coach-participant relationship quality. **Adaptation log:** an existing routine administrative data tool on implementation adaptations and their determinants will be used, completed by Squad Managers who hold regular meetings with individual coaches and collectively with the entire coach cohort. **Coach-to-Coach WhatsApp Group:** the implementing partner routinely establishes a WhatsApp group used by Coaches and the Squad Manager (i.e. not including any clients/participants). Data from this group will include challenges Coaches are facing and solutions suggested by other coaches. Coach phone numbers and any other identifying information derived from these communications will be treated as confidential, stored securely, and handled in accordance with the study's data management plan. **Training observations:** an existing routine administrative data tool will be used to collect semi-structured observations at the initial coach training and at a refresher training after two months of implementation. **Monthly and quarterly implementation reports and follow-up discussions:** these reports will be developed by Population Services International and Matchboxology, providing both quantitative data on reach and their own observations on fidelity, reach, mechanisms of change and implementation strategies and determinants. Monthly reports will be accompanied with a follow-up discussion conducted in English, transcribed through AI transcriptions.

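### The scale-up cost sub-analysis drops start-up costs as research expenses, but the only start-up cost the protocol describes is training, which any roll-out must pay for

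*Protocol*

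**What the plan says.** The opening paragraph of Aim 3 first sets out cost estimates for both arms, to be combined with Aim 1 retention to give an average cost per client retained and an incremental cost per additional person retained. It then adds a sub-analysis that restates those costs for routine care. Its rule and its stated benefit read: "excluding research-related expenses such as start-up and study-specific costs. This will provide more realistic national-level scale-up cost estimates for Coach Mpilo".

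The section on cost and resource use data sources has a category headed Start-up costs. It begins: "Information on the cost of training of coaches and other personnel or volunteers involved in Coach Mpilo will be obtained from Matchboxology". It covers attendance (with the opportunity cost of trainees' time in the economic costing), the cost of organising workshops and the number held, and it ends: "The cost per person trained will consider expenses related to the development of training materials, refreshments, office supplies, facilitator, etc". Nothing other than training appears under that heading.

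Table 1 has a row named Other start-up costs. Its only entry is training for coaches, with the price source given as "Costs from Matchboxology".

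The description of the intervention says that coaches receive one week of structured training from a team that includes a clinical psychologist. Aim 4 plans observations "at the initial coach training and at a refresher training after two months of implementation".

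**The concern.** The sub-analysis should strip out what exists only because a trial is being run and leave what a health department would pay for. Training coaches belongs to the second group. It is how coaches are prepared for the role, the cost data come from the implementing organisation, and every new coach in a national programme would need it. The protocol nevertheless names start-up as an example of a research-related expense, and training is the only thing it files under start-up.

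An analyst who applies the exclusion using the protocol's own categories would therefore cost a programme whose coaches are not trained, while the retention effect from Aim 1 comes from coaches who are. The numerator and denominator of a scale-up ICER would then describe different programmes. The error runs in one direction only, in favour of the intervention, and it affects the figure the protocol presents as the more realistic one for national decisions.

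**Working it through.** **No figure to reproduce.** The protocol gives no unit cost, training cost, coach tenure or ICER. The check compares the sections and then works out how an omitted training cost moves the ICER.

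**Sections side by side.**
- Aim 3, opening paragraph: start-up costs and study-specific costs are two named examples of what is removed, so start-up is not simply another word for study costs.
- Start-up costs category: training of coaches and other programme personnel or volunteers, and nothing else.
- Table 1, Other start-up costs: training for coaches, and nothing else.
- No section defines a research-only start-up category, and none says that training is kept or added back in the sub-analysis.

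**Effect on the ICER.** Let C_I and C_S be the mean cost per participant in the intervention and standard-of-care arms, d the difference in the proportion retained at 12 months, and T the programme training cost per intervention participant.

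- With training: ICER = (C_I − C_S) / d
- Without it: ICER = (C_I − T − C_S) / d
- Shift: T / d, always downward, because T arises in one arm only

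Inputs from the protocol:
- planned difference d = 0.10 (Sample size and power calculations);
- about 800 participants randomised 1:1, so about 800 / 2 = 400 in the intervention arm;
- about 7 coaches (Aim 2, interviews with coaches).

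The values d = 0.05 and d = 0.15 are assumed, to show a range.

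| d | Shift per 1 unit of T | Shift per 1,000 units of training cost per coach |
|---|---|---|
| 0.05 | 1 / 0.05 = 20 | (7 × 1,000 / 400) / 0.05 = 350 |
| 0.10 | 1 / 0.10 = 10 | (7 × 1,000 / 400) / 0.10 = 175 |
| 0.15 | 1 / 0.15 = 6.7 | (7 × 1,000 / 400) / 0.15 = 117 |

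The last column charges all training to the trial's own participants. With annualisation over a longer tenure, T per participant would be smaller.

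**How large might the omitted item be?** This can only be illustrated. Assume that training one coach costs the equivalent of w weeks of coach pay and that a coach works M months. Training as a share of training plus coach pay is w / (w + M × 52/12).
- w = 1, M = 24: 1 / (1 + 104) = 1.0%
- w = 5, M = 6: 5 / (5 + 26) = 16.1%

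Both w and M are assumptions. The share is of training plus coach pay only. It is not a share of incremental cost, which also includes changes in drug, laboratory and clinic costs, so it cannot be read as a percentage error in an ICER.

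**The case against.** The strongest reply is that the governing words are research-related. On that reading start-up means only what was set up for the trial, and the data-source section merely lists where prices come from without deciding what the sub-analysis drops. The word Other in the Table 1 row also suggests that training need not be the whole category. The authors may well have meant this. But the text contains no research start-up category to which the exclusion could attach, and it never says that training stays. The reply explains a possible intention; it does not remove the conflict.

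Three limits do stand.

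- A reader might infer that every ICER in Aim 3 is understated. The documents do not support that. The exclusion is stated only for the sub-analysis. The trial-based incremental cost per additional person retained is introduced before it, with training costs collected in full.
- A reader might also infer that the bias is certain to reach the 20-year model and the HIV Investment Case. No section says which cost set feeds either. The model evaluates a hypothetical national scale-up, so the scale-up cost is a natural input, but that is an inference.
- The refresher is mentioned only as an occasion for observation in Aim 4. It is not labelled start-up, so whether the rule would remove it is unclear.

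Details such as turnover scenarios can reasonably be left to an economic analysis plan. The exclusion itself is fixed in the protocol and has to be corrected there.

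**Conclusion.** The point holds for the routine-implementation sub-analysis and for whatever is built on it. Under the protocol's own categories, the national scale-up cost omits training that a roll-out must incur. The direction is certain if the exclusion is applied as written: the cost per additional man retained falls by T/d, which is 10T at the planned 10-point difference. For cost per life year or per infection averted the direction is the same if this cost set is used, but T/d does not apply and the shift cannot be computed from the document.

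The absolute size is unknown and may be modest. It depends on training cost, coach tenure and caseload, none of which the protocol states in costed form. The primary outcome and its analysis are not affected. The correction should be made, because the affected figure is the one the protocol offers as the more realistic basis for national costing.

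**What to change.** In the opening paragraph of Aim 3, limit the exclusion to costs that exist because of the research: surveys, consent, trial staff time, in-depth interviews and research set-up. State that initial and refresher training of coaches and other programme personnel is kept, annualised over expected coach tenure. This fits the annualisation of multi-year resources already planned under Time horizon and discounting. One-off development of training materials may be shown separately. Align the Start-up costs text and the Table 1 row with this by separating programme start-up from research start-up. State that this cost set is used for any scale-up ICER.

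The price is a change of wording and a small costing step, since training costs are already to be obtained from the implementing organisation. The stated scale-up cost per man will be somewhat higher.

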Appendix
